8.2.2. Secondary Endpoints

8.2.2.1. Change from Baseline in TCD Flow Velocity at Week 48 and Week 96

Change in TCD flow velocity from Baseline to Week 48 and Week 96 will be analyzed with the same MMRM as described for the primary endpoint (change from Baseline in TCD flow velocity at Week 24). A single model will be fit incorporating data from all timepoints.

8.2.2.2. Time to Event Endpoints

TCD flow velocities are categorized as follows:

Normal: < 170 cm/sec

Conditional: 170 to < 200 cm/sec

Abnormal: \geq 200 cm/sec

An abnormal TCD observation in the range of 200 to < 220 cm/sec will require a repeated assessment within 2 to 4 weeks for confirmation of abnormal status (timing based on Principal Investigator clinical judgment). If the confirmatory assessment is < 200 cm/sec, the subject will not be categorized as abnormal for purposes of analysis. An abnormal TCD observation \geq 220 cm/sec will not require a confirmation assessment.

Time to conversion to abnormal will be calculated as number of weeks from date of randomization to the date of TCD assessment when an abnormal TCD flow velocity (\geq 200 cm/sec) is first determined. If the abnormal TCD requires a confirmation assessment, the date of the first abnormal TCD assessment will be used.

For each of the subjects, the time to conversion to abnormal will be right-censored according to the conventions in Table 2.

Summary statistics will include number of subjects with event, number of subjects censored, median time to event along with 95% CI for the median and quartiles. The CIs for the median will be calculated according to Brookmeyer and Crowley (1982) and the CIs for the survival function estimates at fixed time points will be derived using the log-log transformation according to Kalbfleisch and Prentice (2002) (conftype=loglog default option in SAS Proc LIFETEST) with back transformation to a CI on the untransformed scale. The estimate of the standard error will be computed using Greenwood's formula.

For time to conversion to abnormal TCD flow velocity, a log-rank test, stratified for the randomization stratification factors, will be used to test the difference between voxelotor and placebo groups. A Cox proportional hazard model will be used to estimate the hazard ratio, as appropriate. The Kaplan-Meier method will be used to estimate the landmark rates, and the

090177e1a2bf4d41\Approved\Approved On: 31-Jan-2025 17:16 (GMT)

associated 95% confidence intervals at Week 24, Week 48, and Week 96 in voxelotor and placebo groups.

Time to reversion to normal TCD flow velocity (< 170 cm/sec) will be summarized descriptively by treatment group for subjects who achieve a normal TCD flow velocity.

Table 2: Date of Abnormal TCD Event or Censoring

Situation	Date of Abnormal TCD or Censoring	Time to Conversion
Confirmed abnormal TCD event: TCD \geq 200 cm/sec but < 220 cm/sec for first assessment and \geq 200 cm/sec for repeat TCD assessment	Date of first TCD value \geq 200 cm/sec but < 220 cm/sec	Event
Abnormal TCD not requiring confirmation: TCD value \geq 220 cm/sec	Date of TCD assessment \geq 220 cm/sec	Event
No abnormal TCD event observed: All TCD < 200 cm/sec as of data cutoff date TCD \geq 200 cm/sec but < 220 cm/sec for first assessment and < 200 cm/sec for repeat TCD assessment	Date of last TCD assessment with a non-missing value prior to data cutoff date	Censored
Confounding event prior to abnormal TCD: Initiation of postbaseline HU without having experienced an abnormal TCD (either confirmed abnormal TCD event or abnormal TCD event not requiring confirmation) Withdraw from study without having experienced an abnormal TCD (either confirmed abnormal TCD event or abnormal TCD event not requiring confirmation)	Date of last TCD assessment with a non-missing value prior to start of HU or study termination date	Censored
Missing two or more consecutive TCD assessments immediately prior to an observed abnormal TCD: TCD \geq 220 cm/sec immediately after two or more consecutively missed TCD assessments TCD \geq 200 cm/sec but < 220 cm/sec for first assessment and \geq 200 cm/sec for repeat TCD assessment immediately after two or more consecutively missed TCD assessments	Date of last TCD assessment with a non-missing value prior to the two or more consecutively missed TCD assessments	Censored

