8.4.1.2. Secondary Endpoints

The secondary endpoints will be analyzed as described below.

Change from Baseline endpoints

Change in TCD flow velocity from Baseline to Week 48 and Week 96 will be analyzed with the same MMRM as described for the primary endpoint (change from Baseline in TCD flow velocity at Week 24). A single model will be fit incorporating data from all timepoints.

Change in Hb and clinical measures of hemolysis (unconjugated bilirubin, % reticulocytes, absolute reticulocyte, and LDH) from Baseline at Week 24, Week 48, and Week 96 will be analyzed with a similar approach.

TCD responder endpoint

The TCD responder endpoint, defined as a TCD flow velocity reduction from Baseline ≥ 15 cm/sec at a given timepoint, eg, Week 24, Week 48, or Week 96, will be analyzed using an exact Cochran-Mantel-Haenszel (CMH) general association test stratified by the randomization stratification factors for the treatment difference between voxelotor and placebo.

A sensitivity analysis will be performed to assess TCD response definition with various TCD cutoff values in addition to the proposed 15 cm/sec.

Time to event endpoints

For time to conversion from conditional to abnormal TCD, the Kaplan-Meier method will be used to estimate the landmark rates and the associated 95% confidence intervals in the voxelotor and placebo groups at Week 24, Week 48, and Week 96. A log-rank test stratified for the randomization stratification factors will be used to test the difference between voxelotor and placebo groups. A Cox proportional hazard model may be used to estimate the hazard ratio, as appropriate.

Time to conversion to abnormal will be calculated as the number of weeks from the date of randomization to the date of TCD assessment when a TCD flow velocity \geq 200 cm/sec is first observed. For participants who withdraw from the study without conversion to abnormal or who reached analysis data cutoff date without TCD flow velocity reaching abnormal range, their time to conversion to abnormal will be censored at the date of last TCD assessment prior to study withdraw or analysis data cutoff date, as applicable.

Time to reversion from conditional to normal TCD will be analyzed using a similar approach.

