6.4.2.2. Conversion to Abnormal TCD

- For subjects who withdraw from the study or reach analysis data cutoff date without an event (ie, TCD flow velocity reaching abnormal range), their time to conversion to abnormal will be censored at the date of last TCD assessment prior to study withdrawal or analysis data cutoff date, as applicable (Section 8.2.2.2, Table 2).

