6.4.2.3. TCD Responder

A TCD responder is defined as a TCD flow velocity reduction from Baseline ≥ 15 cm/sec, and will be assessed separately at Week 24, Week 48, and Week 96.

- Subjects with a missing TCD flow velocity value at the assessment timepoint will be classified as non-responders.
- Subjects initiating HU postbaseline are to be discontinued from the study. TCD assessments obtained after HU initiation will be excluded from analysis (considered missing).
- RBC transfusions: TCD results within 8 weeks after the transfusion date will be imputed for the analysis of TCD response. Post transfusion results will be imputed by data from the most recent study visit prior to the transfusion (including Baseline) with a non-missing TCD value.

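### Time to conversion to abnormal TCD: an unrepeated 200 to < 220 cm/sec reading is censored or left unclassified, and a repeat taken soon after a transfusion can cancel it

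*SAP*

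**What the plan says.** Protocol 8.4.1.2 runs the time from randomization "to the date of TCD assessment when a TCD flow velocity" of at least 200 cm/sec first appears, with no confirmation step in that definition. The SAP, which by its Section 2 overrides the protocol where they differ, adds one in 8.2.2.2: "An abnormal TCD observation in the range of 200 to < 220 cm/sec will require a repeated assessment within 2 to 4 weeks". It continues: "If the confirmatory assessment is < 200 cm/sec, the subject will not be categorized as abnormal for purposes of analysis". In Table 2 a value of 200 to < 220 is an event only with a repeat of at least 200, and is then dated at the first reading. A value of 220 or more needs no repeat.

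The Table 2 rows for confounding events censor a child at the last non-missing TCD before HU start or study termination. The withdrawal row reads "Withdraw from study without having experienced an abnormal TCD (either confirmed abnormal TCD event or abnormal TCD event not requiring confirmation"; the HU row carries the same condition. For children without an event at withdrawal or cutoff, SAP 6.4.2.2 says "their time to conversion to abnormal will be censored at the date of last TCD assessment prior to study withdrawal or analysis data cutoff date".

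Transfusion is handled for the other TCD endpoints. In SAP 6.4.2.3, "TCD results within 8 weeks after the transfusion date will be imputed for the analysis of TCD response", using the last value before the transfusion; SAP 6.4.2.1 does the same for TCD change. SAP 6.4.2.2 and Table 2 have no transfusion rule.

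SAP 6.3 and 8.2.6 now treat time-to-event results as exploratory: treatment effects with 95% intervals, but no formal test.

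**The concern.** Confirmation can only filter out transient readings if the repeat exists and is interpretable. The rules do not secure either condition.

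Withdrawal or HU start between the reading and its repeat leads to censoring on the day of the abnormal value. That removes the child from the risk set just when conversion has become likely. Protocol 1.1 names HU and chronic transfusion as ways to lower stroke risk once TCD is abnormal, so HU start after such a reading may well be a response to it. Censoring of this kind may be informative.

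The SAP also overrides a post-transfusion TCD value for two TCD endpoints, yet accepts the same value as grounds for discarding an abnormal reading in a third.

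At stake are the reported conversion rates in both arms and, if the loss differs by arm, the hazard ratio.

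**Working it through.** **Step 1. Run cases through Table 2** (210, 205 and 190 cm/sec are illustrative values).

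| Case | Result under the SAP |
|---|---|
| 210, repeat 205 | Event, dated at the 210 reading |
| 210, repeat 190, no transfusion or HU | No event; child stays at risk (intended) |
| 210, withdraws before repeat | Neither confirmed nor exempt from confirmation: censored at last TCD, the 210 reading |
| 210, starts HU before repeat | Same, through the HU row |
| 210 at last visit before cutoff, no repeat, no withdrawal or HU | No row fits: not all values are < 200, and there is no repeat value |
| 210, transfusion, repeat 190 | Handled like the second row; reading cancelled |

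For the cutoff case, SAP 6.4.2.2 does not settle the matter. It equates an event with velocity reaching the abnormal range, which 210 does, while Table 2 makes confirmation a condition of the event.

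For the transfusion case, the repeat comes 2 to 4 weeks after the first reading. A transfusion in that gap precedes the repeat by at most 4 weeks, always inside the 8-week window. Protocol 5.7.3 permits transfusion for surgery or trauma, so the case can arise.

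**Step 2. Reproduce the plan's figures** (SAP 6.1: placebo rate 35% by Week 96, hazard ratio 0.5, 112 per group, 20% dropout).

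- Voxelotor rate: 1 − 0.65^0.5 = 19.4%.
- Events: 112 × (0.350 + 0.194) × 0.8 = 48.7, stated as 49.
- Power by Freedman's formula: Φ(√49 × 0.5/1.5 − 1.96) = 64.6%, stated as about 65%. At two-sided 10%: Φ(2.333 − 1.645) = 75.4%; Protocol 8.2 states about 75%.

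The stated figures hold.

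**Step 3. Illustrate the loss.** The documents do not say how many conversions are first seen at 200 to < 220, or how many of those lack a usable repeat. Assume 80% and 10% to 20%.

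- Events lost: 49 × 0.8 × 0.10 = 3.9; 49 × 0.8 × 0.20 = 7.8. As fractions f of 49: 8% and 16%.
- Censoring a fraction f of events at the event time multiplies the apparent hazard by 1 − f. Placebo Week 96 rate: 1 − 0.65^0.92 = 32.7%; 1 − 0.65^0.84 = 30.4%. If every lost child instead stayed at risk and never converted later: 35% × 0.92 = 32.2%; 35% × 0.84 = 29.4%.
- Standard error of the log hazard ratio, about 2/√events: 2/√49 = 0.286; 2/√45.1 = 0.298; 2/√41.2 = 0.312.

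**Step 4. Hazard ratio.** With losses f_v (voxelotor) and f_p (placebo), the apparent ratio is 0.5 × (1 − f_v)/(1 − f_p). Equal loss leaves 0.50. A 10% loss in placebo only gives 0.5/0.9 = 0.56; in voxelotor only, 0.5 × 0.9 = 0.45. If lost children stay at risk without converting, the figures are ln(0.806)/ln(0.685) = 0.57 and ln(0.826)/ln(0.650) = 0.44.

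The 49 events assume up to 96 weeks of follow-up per child. The study stopped early, so the counts are illustrative only.

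**The case against.** Confirmation is the protocol's own design. Protocol 3.1.1 keeps children at 200 to < 220 in the study pending a repeat, and a normal or conditional repeat may simply show measurement variation. The SAP dates confirmed events at the first reading, so confirmation causes no delay. The endpoint is out of the testing sequence, the loss rates are assumed, and double-blinding with redacted hemoglobin results makes unequal loss less likely. Redefining the event after the Week 48 cutoff analysis, which already included exploratory time-to-event summaries, would be post hoc.

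All of this limits the size of the problem. None of it supplies a rule for a missing repeat at cutoff or explains why a post-transfusion value is usable here only. Blinding does not exclude unequal loss, since withdrawal and transfusion can themselves follow from treatment.

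A reader might infer more than the documents support:

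- That a missing repeat cancels an abnormal reading. The quoted sentence applies only to a repeat that was done and was below 200. The missing-repeat effect comes from the withdrawal and HU rows; at cutoff the case is undefined.
- That true conversions are scored as non-events. Withdrawals and HU starters are censored, not counted as event-free, and a child who stays on study can still convert later. Nor is every unconfirmed reading a true conversion.
- That early termination made the loss large. SAP Section 2 says visits continued after the May 2024 dose pause; nothing shows how many repeats were missed.

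**Conclusion.** The point holds for an exploratory endpoint. Table 2 censors an unrepeated 200 to < 220 reading at its own date when the child withdraws or starts HU, gives no classification at data cutoff, and lets a post-transfusion repeat cancel a reading against the SAP's own 8-week rule for TCD change and response.

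The affected results are the hazard ratio, its interval and the Kaplan-Meier rates. Under an assumed 8% to 16% loss, a 35% placebo rate reads about 33% to 30% and the standard error rises by 4% to 9%. Bias in the hazard ratio requires a loss that differs by arm, and the documents offer no evidence on that.

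One might extend this to the primary result, because SAP 8.2.1 imputes values for children who left the study through conversion to abnormal. The SAP does not say that the Table 2 classification drives that imputation, so no effect on the three formally tested endpoints is shown.

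**What to change.** In SAP 8.2.2.2 and Table 2, for analysis only:

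1. State that a repeat taken within 8 weeks after a red-cell transfusion, or after HU start, cannot cancel a 200 to < 220 cm/sec reading.
2. Add a row for no valid repeat, covering withdrawal, HU start, transfusion and data cutoff.
3. Report the hazard ratio and Kaplan-Meier rates in two versions: with these children censored, and with the first value of at least 200 cm/sec as the event, as in Protocol 8.4.1.2. Label the pair as added after the Week 48 cutoff analysis, so that neither version can be chosen on its result.

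The cost is a wording change, one derived flag from data already collected, and a second set of estimates. Patient care does not change. The downside is that some transient, unconfirmed readings count as events in the second version; reporting both shows how much that matters.

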3.1.1. Study Design

The study will be conducted globally at approximately 50 clinical sites. Study procedures and assessments are outlined in Section 6. The timing of these procedures and assessments are provided in Appendix A, Appendix B, and Appendix C. Dosage and treatment administration are outlined in Section 5.

The study consists of 3 periods (Figure 1):

- · Screening: up to 35 days prior to randomization
- Treatment: 96 weeks
- Follow-Up: 28 days (4 weeks) after the last dose

Approximately 224 participants aged 2 to < 15 years will be randomized 1:1 to voxelotor or placebo.

Participants \geq 12 years old will be administered a fixed dose of voxelotor 1500 mg/day. Participants younger than 12 years of age will receive voxelotor at a weight-based (1500 mg-equivalent) dose, as described in Section 1.6 (Table 1).

Following completion of study treatment, eligible participants will be given the option to enroll in an open label extension study (under a separate protocol) to receive voxelotor for a minimum of 3 years (3 years or until commercial product becomes available or a managed access program, whichever is longer).

At the time of randomization, participants will be stratified by HU use (yes; no), age (2 to ≤ 8 years; > 8 to < 15 years), Screening TCD flow velocity value (170 to < 185 cm/sec; 185 to < 200 cm/sec), and geographic region (Africa including Middle East and North Africa [MENA]; rest of world). Stratification of participants by age was chosen to evenly balance by age distribution using the expected median age of 8 years.

Figure 1: Study Schema

Abbreviations: EOT, end of treatment. Note: Primary endpoint will be assessed at Week 24.

In this study, TCD flow velocities are categorized as follows:

- 1. Normal: < 170 cm/sec
- 2. Conditional: 170 to < 200 cm/sec the eligible participant population for this study
- 3. Abnormal: \geq 200 cm/sec

Enrolled participants with TCD flow velocity values ≥ 200 but < 220 cm/sec may continue in the study and must have a repeat TCD within 2 to 4 weeks (timing based on Principal Investigator clinical judgement). If the repeat TCD flow velocity is abnormal, study drug will be discontinued (see Section 3.4.2 for information on discontinuation requirements) and the participant is required to return for the End of Study (EOS) visit (28 days after the last dose of study drug). Participants will be treated according to local standard of care for abnormal TCD flow velocity.

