3. STUDY OBJECTIVES

Primary Objective:

[figure not shown]
The primary objective is to evaluate the effect of voxelotor compared to placebo on the TCD time-averaged mean of the maximum velocity (TAMMV) arterial cerebral blood flow at 24 weeks in SCD subjects ≥ 2 to < 15 years of age with conditional (170 to < 200 cm/sec) TCD flow velocity.

Secondary Objectives:

[figure not shown]
The secondary objectives are to evaluate the effects of voxelotor compared to placebo on:

- Change in TCD flow velocity at Week 48 and Week 96
- Conversion of TCD category from conditional to abnormal
- Reversion of TCD category from conditional to normal
- Proportion of subjects with TCD response
- Change in Hb over time
- Change in clinical measures of hemolysis
- Annualized incidence rate of vaso-occlusive crises (VOCs)

CCI

CCI

Safety Objective:

The safety objective is to assess the safety and tolerability of voxelotor compared to placebo.

Pharmacokinetic Objective:

The pharmacokinetic objective is to assess the PK of voxelotor as evaluated by population PK (PPK) analysis.

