6. GENERAL STATISTICAL CONSIDERATIONS

6.1. Sample Size and Power

The sample size is planned to provide sufficient statistical power for the primary efficacy analysis and for a robust safety database. In addition, the number of events required to assess the secondary efficacy endpoint of time to conversion to abnormal TCD category is also considered.

For the primary endpoint (change from Baseline in TCD flow velocity [cm/sec]), assuming equal allocation across treatment groups and a common variance, an estimate of the number of subjects in each of 2 treatment groups used the following assumptions in the power calculation:

- Targeted treatment effect: difference in mean change from Baseline in TCD flow velocity is 15 cm/sec
- Common standard deviation is 24 cm/sec
- A significance level of 5% (2 -sided)

Assuming a 20% drop out rate, a sample size of 112 subjects per group provides > 95% power to detect the targeted treatment effect for the following hypothesis test using a Student's t-test:

$$H_0: \mu_1 = \mu_2 \quad \text{vs.} \quad H_A: \mu_1 \neq \mu_2,$$

where μ_1 and μ_2 stand for mean change from Baseline in TCD flow velocity at Week 24 in voxelotor and placebo groups, respectively.

For the secondary efficacy endpoint of time to conversion to abnormal TCD category, assuming 35% of subjects in the placebo group have experienced a TCD flow velocity > 200 cm/sec by Week 96, a hazard ratio of 0.5 between voxelotor group and placebo, a fixed follow up time of up to 96 weeks for each subject, and an overall 20% drop out rate, a total of 49 events is expected. This provides approximately 65% power for a log-rank test at a two-sided significance level of 5% (PASS version 11).

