6.3. Analysis Timing

The primary study analysis was performed after all randomized subjects completed the study through Week 48 or discontinued early, and all data through a corresponding data cut-off date (determined based on the last subject's Week 48 visit date) was entered in the database, reviewed, and verified. This included formal evaluation of the primary Week 24 efficacy endpoint, secondary Week 24 and Week 48 efficacy endpoints, and summary of all safety data through the data cut-off date. Summaries of Week 96 and time to event efficacy endpoints based on partial data available at this time were considered exploratory.

A final study analysis will be performed after the last subject's last visit and final study database lock. Summaries of Week 96 and time to event efficacy endpoints based on partial data will be considered exploratory due to the early termination of the study. The estimated treatment effects (voxelotor vs. placebo) and corresponding 95% CIs will be presented for these endpoints, but without formal hypothesis testing.

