8.2. Efficacy Analyses

Efficacy analyses will be based on the ITT patient population (Section 7), with subjects grouped according to the treatment assigned at randomization. Data from all randomized subjects, regardless of adherence to study drug or to the protocol will be included in the efficacy analyses. This includes data from subjects who discontinued study drug early but continued with study assessments.

Covariate Adjustment

Unless otherwise noted, analyses of primary and secondary efficacy endpoints will be adjusted (see Section 8.2.1 and Section 8.2.2) for the following randomization stratification variables:

- Baseline HU use (yes; no)
- Age (2 years to \leq 8 years; $>$ 8 years to $<$ 15 years)
- Screening TCD value (170 cm/sec to $<$ 185 cm/sec; 185 cm/sec to $<$ 200 cm/sec)

Note: The randomization stratification variable of geographic region (Africa including MENA; rest of world) as stated in the protocol is not included as a covariate as the vast majority of enrolled subjects are from a single region (Africa including MENA).

For stratification variables, the value recorded in the clinical database (ie, per case report form [baseline HU use and age] or by the central reading center [Screening TCD flow velocity]) will be compared to value captured in the IXRS. If differences are observed, the values from the clinical database will be used in the analysis.

Statistical Tests

All statistical tests will be conducted at a two-sided alpha level of 0.05. Adjustment for multiple comparisons is described in Section 8.2.6.

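### Time to reversion to normal TCD is summarised only among children who revert, so it does not compare the randomised groups and conflicts with SAP Sections 6.3 and 8.2

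*SAP*

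**What the plan says.** SAP Section 4.2 lists time to reversion as a secondary endpoint. Section 3 makes the objective comparative: "The secondary objectives are to evaluate the effects of voxelotor compared to placebo on" a list that includes reversion from conditional to normal.

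Section 8.2.2.2 gives conversion to abnormal a full analysis: stratified log-rank test, Cox hazard ratio, Kaplan-Meier landmark rates, and event and censoring rules in Table 2. Reversion gets one sentence: it "will be summarized descriptively by treatment group for subjects who achieve a normal TCD flow velocity". Table 2 covers abnormal TCD only.

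Two other SAP sections bear on the same endpoint:

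- Section 6.3, on the Week 96 and time-to-event efficacy endpoints: "The estimated treatment effects (voxelotor vs. placebo) and corresponding 95% CIs will be presented for these endpoints, but without formal hypothesis testing".
- Section 8.2, on efficacy analyses in general: "Data from all randomized subjects, regardless of adherence to study drug or to the protocol will be included in the efficacy analyses".

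After describing the conversion analysis, Protocol Section 8.4.1.2 says "Time to reversion from conditional to normal TCD will be analyzed using a similar approach". Protocol Section 8.4.3 placed reversion sixth in the test sequence; SAP Section 8.2.6 no longer includes it.

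**The concern.** Reaching a normal velocity is something that happens after randomisation and that the drug is meant to influence. Restricting the summary to children who reach it compares two groups selected by the outcome. If voxelotor works, its reverters include children who would not have reverted on placebo, so the two sets are no longer comparable.

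The restriction also discards the main signal. The effect appears chiefly as more children reverting; among those who do revert within a fixed window, times look much alike in both arms. A real benefit could be reported as a similar time to reversion.

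Conversion adds a second distortion. Under Protocol Section 3.1.1, for a value of at least 200 but below 220 cm/sec, "If the repeat TCD flow velocity is abnormal, study drug will be discontinued" and the child goes to the End of Study visit; at 220 cm/sec or more this happens without a repeat. If voxelotor delays conversion, placebo children have their chance to revert cut off sooner. That shortens the observed times of placebo reverters.

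**Working it through.** **Inputs from the documents.** 112 per arm and 96 weeks of follow-up. For conversion, SAP Section 6.1 assumes "35% of subjects in the placebo group have experienced a TCD flow velocity > 200 cm/sec by Week 96, a hazard ratio of 0.5" for voxelotor against placebo, and 20% dropout.

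**The plan's own time-to-event figure.** Expected conversions = 0.8 × 112 × [0.35 + (1 − 0.65^0.5)] = 48.7, stated as 49. Freedman power at two-sided 5% = Φ(√49 × 0.5/1.5 − 1.96) = Φ(0.373) = 64.6%, stated as about 65%. Both reproduce. They concern conversion; nothing comparable is stated for reversion.

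**Assumptions for reversion (mine).** Placebo reversion p by Week 96 of 10% to 40%, constant hazards, and hazard ratio (HR) above 1 favouring voxelotor.

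**Step 1: no competing event.** With λ = −ln(1 − p)/96 on placebo, HR × λ on voxelotor and follow-up F, the mean time among reverters is 1/λ − F·e^(−Fλ)/(1 − e^(−Fλ)), using each arm's own hazard.

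| F (weeks) | HR | Reverting, placebo vs voxelotor | Mean weeks among reverters |
|---|---|---|---|
| 96 | 1.5 | 20% vs 28.4% | 46.2 vs 45.3 |
| 96 | 2 | 20% vs 36% | 46.2 vs 44.4 |
| 96 | 3.1 | 20% vs 50% | 46.2 vs 42.5 |
| 48 | 2 | 10.6% vs 20.0% | 23.6 vs 23.1 |

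The 48-week row uses the same hazards as the 96-week HR 2 row. It shows that shorter follow-up, as early termination brings, shrinks the gap further.

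**Step 2: precision.** Simulating 4,000 trials (112 per arm, full follow-up, no dropout, p = 20%, HR 2), the 95% CI on the 1.8-week gap has a half-width of about 14.4 weeks. The sign is wrong in about 41% of trials. Comparing the proportions reverting in the same trials has about 76% power.

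A separate simulation (2,000 trials per setting) with 20% dropout and HR 2 measured how often the effect is detected at two-sided 5%:

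| Placebo reversion | Rank test, reverters only | Log-rank, all randomised |
|---|---|---|
| 10% | 5% | 44% |
| 20% | 6% | 74% |
| 30% | 8% | 87% |
| 40% | 10% | 95% |

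Power is used here only to measure information retained; the SAP plans no test.

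**Step 3: add conversion as a competing event.** Conversion hazards are c₀ = −ln(0.65)/96 on placebo and c₁ = 0.5 × c₀ on voxelotor. With r the reversion hazard and h = r + c, P(revert) = (r/h)(1 − e^(−96h)), and the mean among reverters is the Step 1 formula with h in place of λ and F = 96. Here p is the placebo reversion that would occur without conversion.

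| p | HR | Reverting, placebo vs voxelotor | Mean weeks among reverters | Direction |
|---|---|---|---|---|
| 10% | 2 | 8.2% vs 17.2% | 43.7 vs 44.6 | wrong |
| 20% | 1.5 | 16.4% vs 25.7% | 42.8 vs 43.6 | wrong |
| 20% | 2 | 16.4% vs 32.6% | 42.8 vs 42.7 | flat |
| 30% | 2 | 24.7% vs 46.5% | 41.8 vs 40.7 | right |

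**The case against.** Nobody disputes what the sentence says. The case against is about weight.

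- **Exploratory endpoint, terminated study.** True. But Section 6.3 withdraws only the formal test for such endpoints; it keeps the effect estimates and CIs. Incomplete follow-up makes censoring rules more necessary.
- **The SAP supersedes the protocol.** SAP Section 2 says so, and the departure from the protocol is not in itself an error. The conflict that matters is inside the SAP.
- **The number of reverters would probably be shown.** Likely, and a crude proportion could then be worked out from the arm sizes. The table mock-ups are in a separate document. Still, the SAP commits to no denominator or CI. Its sentence on numbers with events and censored follows the conversion-only censoring rule, and a reverters-only set has nobody censored.
- **The responder endpoint carries related information.** In part. From a baseline below 185 cm/sec, a fall of at least 15 must end below 170; a fall of at least 30 does so from any eligible baseline. But these are judged at fixed visits and are not necessary for reversion: a child at 172 can revert without responding.
- **The wrong-direction cases are weak.** Agreed. The shifts are under one week. With 112 per arm the half-widths are about 22 and 16 weeks, and the wrong sign occurs in about 53% to 55% of trials. Attenuation is the supportable claim; systematic reversal is not.

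**Conclusion.** The concern holds. As written, Section 8.2.2.2 specifies an analysis that cannot answer the stated objective and cannot be reconciled with Sections 6.3 and 8.2. It should be fixed.

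The main consequence is strong attenuation: a 16-point difference in the proportion reverting becomes a 1.8-week difference in means with a CI of about ±14 weeks. The direction can also be wrong by chance, if the effect builds slowly, or through earlier conversion on placebo. It does not reverse systematically under proportional hazards with equal follow-up.

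The sizes rest on assumed reversion rates, constant hazards and continuously observed times, whereas TCD is measured at visits. The conflict in the text depends on none of these. The primary result, the test sequence and the type I error rate are unaffected.

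**What to change.** Replace the reversion sentence in SAP Section 8.2.2.2 with a rule set along these lines:

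> Time to reversion will be analysed in the ITT population as an exploratory endpoint without formal testing. The event is the first TCD below 170 cm/sec after randomisation; no confirmation is needed. A TCD in the 8 weeks following an RBC transfusion is replaced as in Section 6.4.2.3 and cannot itself be an event. Conversion to abnormal (Table 2) before reversion is a competing event. All other subjects are censored at their last non-missing TCD before HU start, study withdrawal or data cutoff. By arm, report the number and proportion reverting among all randomised subjects, and the cumulative incidence at Weeks 24, 48 and 96 with 95% CI. Also report the cause-specific hazard ratio with 95% CI from a Cox model stratified by the Section 8.2 factors.

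The transfusion rule is borrowed from the responder endpoint ("TCD results within 8 weeks after the transfusion date will be imputed for the analysis of TCD response"), because Table 2 has none. Two further points need a stated choice: whether Table 2's rule on two or more consecutive missed assessments applies, and whether TCDs after the dose pause count. Section 8.2 implies that they do; an exclusion like the one in Section 8.2.8 could be a sensitivity analysis.

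Other analyses of all randomised subjects would also remove the conflict. The minimum is to count everyone, state the censoring, and give an effect with its CI.

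The cost is a short paragraph and some code for cumulative incidence; the Cox code carries over from conversion. No new data are needed. Because the primary study analysis has already been done (Section 6.3), label the result exploratory or report it as an additional analysis under Section 10.
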